### 10.3 Management of Pruritus

If an event of pruritus is reported by subjects in this study, the location and intensity of the event must be captured on the eCRF as an AE. In addition, as listed below, two separate scales will be used to assess pruritus in subjects who report itching.

- An itch visual analog scale (VAS) will be used to record the intensity of the event (*Furie et al., 2013*). Site personnel should instruct the subject to draw a line on the scale corresponding to the maximum intensity of itch.
- The 5-D itch scale is a multidimensional questionnaire completed by subjects assessing pruritus. The 5D-itch scale includes a range of 0 (no itch) to 10 (worst imaginable itch) covering five dimensions: degree, duration, direction, disability and distribution.

If reported, pruritus should be assessed at each visit until resolution of the event. The scales should be completed by the subject/site personnel during each assessment/visit where pruritus is reported.

[REDACTED]

## 11. STATISTICAL CONSIDERATIONS

### 11.1 General Considerations

All data will be mapped into the appropriate SDTM domains per version 3.2. All analysis datasets will be in the appropriate ADaM data structure. Pinnacle21 will be used to ensure compliance of the SDTM domains and ADaM datasets to CDISC standards.

All quantitative endpoints will be summarized using an 8-number summary (n, mean, standard deviation, median, 25th quartile, 75th quartile, minimum and maximum values). All qualitative endpoints will be summarized by the number of subjects meeting the endpoint and the percentage of subjects out of the appropriate population. The denominator will be displayed when needed.

Statistical inference will be performed as appropriate. Only two-sided test with an  $\alpha=0.05$  will be used.

### 11.2 Sample Size Considerations

The planned sample size is approximately 105 subjects. Group sample sizes of 45 in each active arm and 15 in the placebo arm achieve 83.552% power to detect a ratio of the group proportions of 40%. The proportion in the smallest active arm is assumed to be 0.4000 under the null hypothesis and 0.0400 under the alternative hypothesis. The proportion in the placebo arm is 10%. The test statistic used is the two-sided Mantel-Haenszel test. The significance level of the test is 0.05. To account for a 10% discontinuation rate, 14 additional subjects will be enrolled to attempt to have 105 who complete treatment, bringing the total number of subjects enrolled to 119.

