### 4.2.2 Justification of EDP-305 Dose

This phase 2 trial has been designed to assess the efficacy, safety and tolerability of 2 doses (1 mg, and 2.5 mg) of EDP-305 in patients with PBC so as to provide proof of concept data to support Phase 3 in this indication.

Study EDP 305-001 characterized a broad range of single and multiple doses: from 1 to 80 mg in the SAD part, and from 0.5 to 20 mg in the MAD part, and administered as an oral suspension. The safety and tolerability of EDP-305 has been established not only in healthy subjects but also in subjects with presumptive NAFLD at doses up to 80 mg single dose and up to 20 mg once daily for 14 consecutive days.

As demonstrated in study EDP 305-001, EDP-305 was generally well tolerated at single doses up to 80 mg and at multiple doses up to 20 mg for 14 days. No SAEs or Grade 4 AEs were reported. No clinically significant laboratories were reported except one transient Grade 2 ALT/AST elevation in n=1 (MAD-HV-20mg) that led to drug discontinuation. Drug related pruritus was reported after multiple dosing at the higher doses of EDP-305 10 mg (n=2) and 20 mg (n=7), and PBO (n=1), with 1 discontinuation at 20 mg in HV. Total, LDL-, HDL- cholesterol and triglycerides did not differ between EDP-305 and placebo in healthy at any dose or PN subjects at any dose, except for cholesterol and HDL at 20mg.

The pharmacokinetics of EDP-305 was profiled over a broad range of single and multiple doses. A dose proportional increase in exposure was observed over the broad dose range studied. Half-life ranged from 11-16 hours and from 10-23 hours following single and multiple doses of EDP-305, respectively. There was more drug accumulation observed following 20 mg dose compared to lower doses, indicating a potential change in the PK profile at 20 mg.

[REDACTED]

Based on observed safety profile to date, pharmacokinetics profile and changes in C4 and FGF-19 in study EDP 305-001 and relative bioavailability data from study 006, (Section 1.4.2.4), EDP-305 doses of 1 and 2.5 mg once daily using the tablet formulation are selected for this study. The exposures associated with this dose range are expected to result in clinically meaningful changes in C4 and other relevant markers of FXR activity (FGF-19), while minimizing the incidence of potential adverse events (i.e. pruritus).

[REDACTED]

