## **11.5 Efficacy Endpoints**

### **11.5.1 Primary Efficacy Endpoints**

The primary efficacy endpoint of the study is the proportion of subjects with at least 20% reduction in ALP from pre-treatment values or normalization of ALP at Week 12. The denominator will be the number of subjects in the efficacy population (missing=failure). Treatment comparisons will be made using a Mantel-Haenszel test comparing each of the active treatment arms to placebo, separately.

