The total maximum length of time of participation for each subject enrolled in the study will be approximately 20 weeks based on a maximum of 28 days for the Screening Period, 12 weeks for the Treatment Period and 4 weeks for the Follow-up Period.

The planned sample size is approximately 105 subjects. Group sample sizes of 45 in each active arm and 15 in the placebo arm achieve 83.552% power to detect a ratio of the group proportions of 40%. The proportion in the smallest active arm is assumed to be 0.4000 under the null hypothesis and 0.0400 under the alternative hypothesis. The proportion in the placebo arm is 10%. The test statistic used is the two-sided Mantel-Haenszel test. The significance level of the test is 0.05.

To account for a 10% discontinuation rate, 14 additional subjects will be enrolled to attempt to have 105 who complete treatment, bringing the total number of subjects enrolled to 119.

PASS software version 14 was used to calculate the sample size.

Subjects will be asked to participate in the PK/PD substudy. The randomization schedule will be developed to allow for balance between the treatment groups within the substudy. For all non-PK/non-PD analysis purposes, the subjects in the substudy will be combined with the subjects not in the substudy.

In order to achieve this balance subjects will be stratified by:

- 1) prior use of fibrates
- 2) prior and/or current use of UDCA

Note that both 1) and 2) may be applicable for a given subject. In addition, a subset of subjects will be included in the PK/PD substudy.

Subjects will be randomized to 3 treatment groups in a 3:3:1 ratio after stratification:

- Treatment Group 1: EDP-305 1 mg orally for 12 weeks
- Treatment Group 2: EDP-305 2.5 mg orally for 12 weeks
- Treatment Group 3: Placebo (PBO) orally for 12 weeks

A minimum of 10 subjects per treatment group will be included in the PK/PD substudy.

Triangle Biostatistics generated the randomization schedule and provided it to Bioclinica as the IWRS vendor, for incorporation into the IWRS

6 Statistical Considerations

All analyses will use SAS version 9.4 or higher.

Continuous and discrete variables will be summarized using an 8-number summary (n, mean, standard deviation, median, 25th quartile, 75th quartile, minimum and maximum values). The median, minimum and maximum values will be displayed to the same level of precision as the raw data, the mean to one additional decimal place and the SD to two additional decimal places.

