9.1.2 Analysis of Primary Endpoint

For the primary endpoint, the Cochran-Mantel-Haenszel (CMH) test will be used to compare the proportion of subjects with ALP Response = "Yes" (percent improvement < -0.20 and/or normalization at Week 12 from Baseline) for each of the active treatment groups to placebo. The CMH test will be stratified, two-sided with an alpha level at 0.05. For the stratification in this analysis, the two randomization strata (fibrates and UDCA use) will be combined to create one strata variable. The code used to generate the p-value for each active treatment vs the placebo will be (with necessary output steps added):

Proc freq data=*indata*;

Tables strata*treatment*response/cmh;

Run;

The primary analysis of the primary endpoint will be performed using the Full Efficacy population. The analysis will be repeated on the Per-Protocol (PP) population, including only subjects with Baseline and Week 12 ALP results.

Subgroup analysis will be performed for ALP Response for the following subgroups:

- Age (<65 vs ≥65)
- gender
- UDCA strata
- Prior use of Fibrates strata
- ALP baseline categories [1.67xULN,2xULN), [2xULN,3xULN), [3xULN,4xULN), [4xULN,5xULN), and ≥5xULN (categories are data dependent)
- Total Bilirubin baseline categories [1xULN,2xULN), [2xULN,3xULN), ≥3xULN (categories are data dependent)
- ALP/Total Bilirubin/UDCA baseline subgroup (categories are data dependent, cut points should be based on median baseline values)
 - ALP≤3xULN, Total Bilirubin≤2xULN, UDCA usage,
 - ALP≤3xULN, Total Bilirubin>2xULN, UDCA usage
 - ALP>3xULN, Total Bilirubin≤2xULN, UDCA usage,
 - ALP>3xULN, Total Bilirubin>2xULN, UDCA usage
 - ALP≤3xULN, Total Bilirubin≤2xULN, No UDCA usage,
 - ALP≤3xULN, Total Bilirubin>2xULN, No UDCA usage
 - ALP>3xULN, Total Bilirubin≤2xULN, No UDCA usage,
 - ALP>3xULN, Total Bilirubin>2xULN, No UDCA usage

The code used to generate the p-value for each active treatment vs the placebo will be:

Proc freq data=*indata*;

Tables *subgroup**treatment*response/cmh;.

Run;

The subgroup analysis will be performed using the Full Efficacy population

The proportion of responders will be summarized and plotted by Visit.

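### The stated 83.552% power does not hold at the stated 10% placebo rate (about 60% per dose); it matches active 40% versus placebo 4%, so the intended placebo rate must be stated

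*Protocol*

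**What the plan says.** Protocol 11.2 states: "Group sample sizes of 45 in each active arm and 15 in the placebo arm achieve 83.552% power". The effect is described as the power "to detect a ratio of the group proportions of 40" percent. The rates follow: "The proportion in the smallest active arm is assumed to be 0.4000 under the null hypothesis and 0.0400 under the alternative hypothesis". Then: "The proportion in the placebo arm is 10" percent. The test is a two-sided Mantel-Haenszel test at 0.05. The Protocol synopsis and SAP section 5 repeat the paragraph word for word, and the SAP adds: "PASS software version 14 was used to calculate the sample size".

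The power refers to one dose against placebo. Protocol 11.5.1 says: "Treatment comparisons will be made using a Mantel-Haenszel test comparing each of the active treatment arms to placebo, separately". SAP 9.1.2 keeps that comparison and adds stratification: "The CMH test will be stratified, two-sided with an alpha level at 0.05". SAP 6.4 makes no multiplicity adjustment, so each comparison is tested at the full 0.05.

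**The concern.** The inputs contradict one another. A null hypothesis for this comparison is that active equals placebo, yet the paragraph gives the active arm 40% under the null. Under the alternative it gives the active arm 4%, which is below the stated placebo rate of 10%. No pairing of the three rates gives a ratio of 40% except 0.04/0.10, where the drug is worse than placebo.

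The natural repair is to read the paragraph as active 40% against placebo 10%. The design then has nowhere near 83.6% power.

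This matters because Protocol 4.2.2 says the trial is run "so as to provide proof of concept data to support Phase 3 in this indication". A reader who accepts 83.6% power at a 10% placebo rate would expect an effective dose to miss significance in about 16% of trials, and could read too much into a non-significant dose comparison.

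**Working it through.** **Inputs.** From Protocol 11.2: n₁ = 45 (one active dose), n₂ = 15 (placebo), N = 60, two-sided alpha 0.05 (z = 1.96), and candidate rates 0.40, 0.04 and 0.10. From Protocol 11.5.1: each dose is compared with placebo separately.

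**Formula.** Normal approximation for the Mantel-Haenszel test, with p̄ = (n₁p₁ + n₂p₂)/N:

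- SE₀ = √[ N/(N−1) × p̄(1−p̄)(1/n₁ + 1/n₂) ]
- SE₁ = √[ N/(N−1) × ( p₁(1−p₁)/n₁ + p₂(1−p₂)/n₂ ) ]
- Power = Φ( (|p₁−p₂| − 1.96 × SE₀) / SE₁ )

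**Step 1: reproduce the printed figure (active 0.40, placebo 0.04).**
- p̄ = (18 + 0.6)/60 = 0.310; SE₀ = 0.13905; SE₁ = 0.08959
- Power = Φ((0.36 − 1.96 × 0.13905)/0.08959) = Φ(0.976) = 0.835518, which rounds to 83.552%.

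Solving the same formula for the placebo rate that gives 83.552% returns 4.000%. A search over all pairs of rates in steps of 0.01 (pooled, Mantel-Haenszel and unpooled normal forms) finds only 0.40/0.04 and its mirror image 0.60/0.96. Also, 0.04/0.40 = 10%, so the printed 10% may be the ratio of the two rates and not the placebo rate.

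**Step 2: the stated placebo rate (active 0.40, placebo 0.10).**
- p̄ = (18 + 1.5)/60 = 0.325; SE₀ = 0.14082; SE₁ = 0.10736
- Power = Φ((0.30 − 1.96 × 0.14082)/0.10736) = Φ(0.224) = 0.588.

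**Step 3: does the choice of approximation matter?**

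| Method (45 vs 15, two-sided 0.05) | 40% vs 10% | 40% vs 4% |
|---|---|---|
| MH normal, N/(N−1) in both variances | 58.8% | 83.552% |
| MH normal, N/(N−1) in null variance only | 58.9% | 83.8% |
| Pooled normal, no N/(N−1) factor | 59.8% | 84.4% |
| Exact enumeration of the one-stratum MH test | 62.7% | 87.5% |

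At 10% placebo every Mantel-Haenszel or pooled form falls short, by between 83.6 − 62.7 = 20.9 and 83.6 − 58.8 = 24.8 points. Taken literally (active 4%, placebo 10%), power is 15% to 20%, in the wrong direction.

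**Step 4: sensitivity to the placebo rate.** With active at 40%, in the form used in Step 1:

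| Placebo rate | 4% | 5% | 6% | 8% | 10% |
|---|---|---|---|---|---|
| Power | 83.6% | 79.6% | 75.5% | 67.1% | 58.8% |

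Among 15 placebo subjects, 4% is 0.6 expected responders and 10% is 1.5. Less than one expected responder separates the two ends of this table.

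**Step 5: stratification.** The figures above are unstratified, whereas SAP 9.1.2 stratifies by fibrate and UDCA use. The documents give no stratum sizes, so the check needs an assumption: simulations of 200,000 trials per setting used stratum shares from 90/10 to four equal strata, with the same response rates in each stratum. Power was 60–62% at 40% versus 10%, and 85–87% at 40% versus 4%. Stratification does not close the gap.

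**The case against.** The strongest reply is that this is a wording error around a sound calculation. The only digit-for-digit match is 40% versus 4%, so the sponsor probably computed 83.552% correctly and then mislabelled the inputs. That is the likelier reading, but it is an inference. The exact match depends on placing the N/(N−1) factor in both variances, and the PASS output is not available. If 4% was intended, the documents still print the wrong placebo rate in three places, and no reason is given for either rate.

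A second point stands in part. The 45 and 15 are completer targets, whereas the primary analysis (Protocol 11.5.1, SAP 9.1.1) counts every dosed subject, with missing treated as failure. With 119 enrolled at 3:3:1 the arms are 51/51/17. If 40% and 10% are the rates in that population, power is 65.8% (MH normal) to 68.0% (exact). If they are completer rates and 10% of each arm drops out as failures, the rates become 36% and 9%, and power is 57.5% to 60.9%. Neither comes near 83.6%.

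Third, this is a proof-of-concept trial with two chances to succeed. If both doses truly reach 40% against 10%, the probability that at least one is significant at 45/45/15 is about 75%. That is true, but it is not the quantity the plan states and it still falls short of 83.6%. It is also fair to say that planned power does not change any estimate, confidence interval or p-value.

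**Conclusion.** The concern holds. At 45 versus 15, two-sided 0.05, Mantel-Haenszel, the printed power and the printed placebo rate are incompatible. If the true rates are 40% and 10%, power is about 60% per dose (58.8% to 62.7%), and an effective dose misses significance in about 37% to 41% of trials, against the 16% implied. If the intended placebo rate is 4%, the printed power stands and the text is wrong. In that case the plan depends on a low placebo rate that it neither states as such nor justifies.

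The figures assume the sample sizes as printed, an active rate of 40%, and no stratification; the simulations under assumed strata agree. That 4% was the value entered in PASS is a strong inference from the arithmetic, not something the documents show. The test, alpha and estimates are unaffected.

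**What to change.** 1. Check the PASS 14 output for the placebo rate that was entered.
2. State the intended placebo rate, 4% or 10%, with a justification.
3. Rewrite the paragraph in the Protocol synopsis, Protocol 11.2 and SAP section 5, with the null as active = placebo and one of these alternatives:
   - *Placebo 10%:* Alternative: active 40% versus placebo 10% (ratio 4). With 45 versus 15 subjects and a two-sided 0.05 Mantel-Haenszel test, power is about 60% for each dose-versus-placebo comparison.
   - *Placebo 4%:* Alternative: active 40% versus placebo 4% (ratio 10). With 45 versus 15 subjects and a two-sided 0.05 Mantel-Haenszel test, power is 83.6% for each dose-versus-placebo comparison, falling to about 60% if the placebo rate is 10%.

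The cost is one look at the PASS file and one corrected paragraph in three places. Correcting the statement requires no change to the design, sample size, test or alpha. The sponsor must, however, accept either a stated power of about 60% or an explicit reliance on a 4% placebo rate.

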### 11.3 Analysis Populations

The following analysis populations are planned:

- *Safety Population*: All subjects who receive at least one dose of study medication. Subjects will be included in the treatment group that corresponds to the study medication received during the study.
- *Efficacy Population*: All subjects who receive at least one dose of study medication. Subjects will be included in the randomized treatment group.
- *Pharmacokinetic Population*: All subjects receiving active study medication and having any measurable plasma concentration of study medication at any timepoint.

## **11.4 Subject Disposition and Demographic Data**

The number of subjects screened, randomized, randomized and treated, randomized and not treated, in the safety population, in the efficacy population, and in the PK population will be summarized. The denominator for the calculation of percentages will be from the number of subjects randomized.

The following categories will also be summarized for subject disposition:

- Completed study drug per protocol
- Discontinued study drug early and the reason for discontinuation
- Completed the study
- Discontinued from the study early and the reason for discontinuation

Subject demographics will be summarized by randomized treatment group for all subjects in the safety population. Appropriate baseline characteristics will be included in addition to demographic characteristics. No statistical testing will be performed. Additional details will be provided in the Statistical Analysis Plan.

## **11.5 Efficacy Endpoints**

### **11.5.1 Primary Efficacy Endpoints**

The primary efficacy endpoint of the study is the proportion of subjects with at least 20% reduction in ALP from pre-treatment values or normalization of ALP at Week 12. The denominator will be the number of subjects in the efficacy population (missing=failure). Treatment comparisons will be made using a Mantel-Haenszel test comparing each of the active treatment arms to placebo, separately.

### **11.5.2 Secondary Efficacy Endpoints**

The secondary efficacy endpoints are as follows:

- Bilirubin (Total, Conjugated, Unconjugated) decline from Baseline at Week 12
- Change from Baseline in Alanine aminotransferase (ALT), Aspartate aminotransferase (AST), and Gamma-Glutamyl transferase (GGT) at Week 12
- Change from Baseline of noninvasive liver fibrosis markers (Enhanced Liver Fibrosis [ELF] panel, PRO C3, AST to Platelet Ratio Index [APRI] and fibrosis-4 [FIB-4]) at Week 12
- Change from Baseline in fibrinogen, CRP, IL6, IL1 $\beta$ , TNF- $\alpha$ , TNF- $\beta$ , alpha2 macroglobulin and haptoglobin levels at Week 12

- Change from Baseline in Triglycerides (TG), Total Cholesterol (TC), High Density Lipoprotein Cholesterol (HDL-C), Low Density Lipoprotein Cholesterol (LDL-C) at Week 12
- Change from Baseline in 5D-itch scale and Visual Analog Score (VAS) at Week 12
- Change from Baseline in PBC-40 Quality of Life (QoL) at Week 12
- Pharmacodynamic parameters of EDP-305: FGF19, C4 and Bile Acid (BA) at week 12

Each endpoint will be summarized using an 8-number summary. Subjects in the efficacy population will be included. Comparisons of treatment arms will be performed using an analysis of covariance (ANCOVA) model with treatment and baseline values included in the model where appropriate.

## **11.6 Safety Endpoints**

### **11.6.1 Adverse Events**

Adverse events will be summarized by MedDRA system organ class and preferred term by treatment group. All subjects in the safety analysis set will be included in the summaries. No statistical testing will be performed.

Summaries of Adverse Events will include the following:

- An overall summary of AEs with a line for each of the categories provided below.
- Treatment-emergent adverse events
- Treatment-emergent treatment-related adverse events
- Treatment-emergent adverse events leading to study drug discontinuation
- Serious adverse events
- Serious treatment-related adverse events
- Adverse events leading to death

### **11.6.2 Clinical Laboratory Data**

Summaries of clinical laboratory results will be performed using an 8-number summary by visit and treatment. All subjects in the safety population will be included in these summaries.

The number and percentage of subjects with treatment-emergent laboratory abnormalities will be summarized by treatment group. In addition, shift from baseline tables will be generated by visit and treatment group.

Change from Baseline will be included in summary tables for laboratory parameters. Shift tables will also be generated for safety laboratory parameters by visit and treatment group. All

laboratory data will be included in the data listings and all test values outside the normal range will be flagged.

### **11.6.3 Electrocardiogram (ECG) Data**

ECG data will be summarized using an 8-number summary by visit and treatment. Change from Baseline will be included in summary tables for ECG parameters. In addition, the number and percentage of subjects with significant changes in ECG parameters will be summarized by treatment. No statistical testing will be performed.

### **11.6.4 Vital Signs**

Vital signs data will be summarized using an 8-number summary by visit and treatment. In addition, the number and percentage of subjects with significant changes in vital signs will be summarized by treatment. Change from Baseline will be included in summary tables for vital signs. No statistical testing will be performed.

### **11.6.5 Concomitant Medications**

The number and percentage of subjects taking concomitant medications will be summarized by drug class and drug name. Subjects in the safety population will be summarized by treatment group. No statistical testing will be performed.

